**15 Safety and Adverse Events (Appendix H)****15.1 Definitions****Adverse Event**

An *adverse event* (AE) is any noxious, unintended, or untoward medical occurrence that may appear or worsen in a subject during the course of a study. It may be a new intercurrent illness, a worsening concomitant illness, an injury, or any concomitant impairment of the subject's health, including laboratory test values (as specified by the criteria below), regardless of etiology. Any worsening (i.e., any clinically significant adverse change in the frequency or intensity) of a pre-existing condition should be considered an AE. A diagnosis or syndrome should be recorded on the AE page of the case report forms (CRF) rather than the individual signs or symptoms of the diagnosis or syndrome.

Abnormal results of diagnostic procedures are considered to be adverse events if the abnormality:

- results in study withdrawal
- is associated with a serious adverse event
- is associated with clinical signs or symptoms
- leads to additional treatment or to further diagnostic tests
- is considered by the investigator to be of clinical significance

**Serious Adverse Event**

A serious adverse event (SAE) is one that at any dose (including overdose):

- Results in death
- Is life-threatening
- Requires inpatient hospitalization or prolongation of existing hospitalization
- Results in persistent or significant disability or incapacity
- Results in a congenital anomaly or birth defect
- Is an important medical event

Important medical events are those that may not be immediately life threatening, but are clearly of major clinical significance. They may jeopardize the subject, and may require intervention to prevent one of the other serious outcomes noted above.

An overdose, accidental or intentional, whether or not it is associated with an AE, or abuse, withdrawal, sensitivity or toxicity to an investigational product should be reported as an AE. If an overdose is associated with an AE, the overdose and adverse event should be reported as separate terms.

All subjects will be monitored for AEs during the study. Assessments may include monitoring of any or all of the following parameters: the subject's clinical symptoms, laboratory, pathological, radiological or surgical findings, physical examination findings, or other appropriate tests and procedures.

#### ***Adverse Event Reporting Period***

All AEs will be recorded by the Investigator from the time the subject signs informed consent to 7 days after the last dose (completion of the 4th week). AEs and SAEs will be recorded on the AE page of the CRF and in the subject's source documents. All SAEs must be reported within 24 hours of the Investigator's knowledge of the event by facsimile, or other appropriate method, using the SAE Report Form, or approved equivalent form.

#### ***Preexisting Condition***

Any worsening (i.e., any clinically significant adverse change in the frequency or intensity) of a pre-existing condition should be considered an AE.

#### ***General Physical Examination Findings***

At screening, any clinically significant abnormality should be recorded as a preexisting condition. At the end of the study, any new clinically significant findings/abnormalities that meet the definition of an adverse event must also be recorded and documented as an AE.

#### ***Post-study Adverse Event***

---

 "Life-threatening" means that the subject was at immediate risk of death at the time of the serious adverse event; it does not refer to a serious adverse event that hypothetically might have caused death if it were more severe.

 "Persistent or significant disability or incapacity" means that there is a substantial disruption of a person's ability to carry out normal life functions.

 Medical and scientific judgment should be exercised in deciding whether expedited reporting is appropriate in situations where none of the outcomes listed above occurred. Important medical events that may not be immediately life-threatening or result in death or hospitalization but may jeopardize the subject or may require intervention to prevent one of the other outcomes listed in the definition above should also usually be considered serious. Examples of such events include allergic bronchospasm requiring intensive treatment in an emergency room or at home, blood dyscrasias or convulsions that do not result in patient hospitalization, or the development of drug dependency or drug abuse. A new diagnosis of cancer during the course of a treatment should be considered as medically important.

All unresolved AEs should be followed by the investigator until the events are resolved, the subject is lost to follow-up, or the AE is otherwise explained. At the last scheduled visit, the investigator should instruct each subject to report any subsequent event(s) that the subject, or the subject's personal physician, believes might reasonably be related to participation in this study. The investigator should notify the study sponsor of any death or AE occurring at any time after a subject has discontinued or terminated study participation that may reasonably be related to this study.

### ***Abnormal Laboratory Values***

A clinical laboratory abnormality should be documented as an AE if any one of the following conditions is met:

- The laboratory abnormality is not otherwise refuted by a repeat test to confirm the abnormality
- The abnormality suggests a disease and/or organ toxicity
- The abnormality is of a degree that requires active management; e.g. change of dose, discontinuation of the drug, more frequent follow-up assessments, further diagnostic investigation, etc.

### ***Hospitalization, Prolonged Hospitalization or Surgery***

Any AE that results in hospitalization or prolonged hospitalization should be documented and reported as a SAE unless specifically instructed otherwise in this protocol. Any condition responsible for surgery should be documented as an AE if the condition meets the criteria for an AE.

Neither the condition, hospitalization, prolonged hospitalization, nor surgery are reported as an AE in the following circumstances:

- Hospitalization or prolonged hospitalization for diagnostic or elective surgical procedures for a preexisting condition. Surgery should *not* be reported as an outcome of an AE if the purpose of the surgery was elective or diagnostic and the outcome was uneventful.
- Hospitalization or prolonged hospitalization required to allow efficacy measurement for the study.
- Hospitalization or prolonged hospitalization for therapy of the target disease of the study, unless it is a worsening or increase in frequency of hospital admissions as judged by the clinical investigator.

## **15.2 Recording of Adverse Events (Appendix H)**

At each contact with the subject, the investigator must seek information on adverse events by specific questioning and, as appropriate, by examination. Toxicity will be scored using the NCI CTCAE, Version 5.0. A copy of the CTCAE, Version 5.0, can be downloaded from [https://ctep.cancer.gov/protocolDevelopment/electronic\\_applications/ctc.htm#ctc\\_50](https://ctep.cancer.gov/protocolDevelopment/electronic_applications/ctc.htm#ctc_50). All appropriate treatment areas should have access to a copy of the CTCAE, Version 5.0. All adverse clinical experiences, whether observed by the investigator or reported by the subject, must be recorded, with details about the duration and intensity of each episode, the action taken with respect to the test drug, and the subject's outcome. The investigator must evaluate each adverse experience for its relationship to the test drug and for its seriousness.

The study sponsor shall notify the FDA by telephone or by facsimile transmission of any unexpected fatal or life-threatening experience associated with the use of the drug as soon as possible but no later than 7 calendar days from the sponsor's original receipt of the information.

All other SAEs that meet the criteria for reporting to the FDA must be reported to the FDA within 15 calendar days after awareness of the event. A clear description of the suspected reaction should be provided along with an assessment as to whether the event is drug or disease related.

## **15.4 Stopping Rules**

The stopping rules are as follows:

Scenario 1: The occurrence of extrapyramidal symptoms, symptoms suggestive of tardive dyskinesia (including vermicular movements of the tongue), neuroleptic malignant syndrome or any SAE or treatment-emergent AE  $\geq$  Grade 3 felt to be causally related to TFP in a single subject:

- Rule: Treatment will be immediately stopped in that subject and the subject will be discontinued from the study.

Scenario 2: The occurrence of the extrapyramidal symptoms, symptoms suggestive of tardive dyskinesia (including vermicular movements of the tongue), neuroleptic malignant syndrome or the same SAE or treatment-emergent AE  $\geq$  Grade 3 felt to be causally related to TFP in more than 1 subject:

- Rules:
  - a. Treatment will be immediately stopped in those subjects and those subjects will be discontinued from the study.
  - b. If the 2 or more subjects are in Cohort A, the trial will be stopped; no MTD will be declared.
  - c. If the 2 or more subjects are in Cohort B, the study will be stopped, and 1 mg/day will be declared the MTD.

- d. If the 2 or more subjects are in Cohort C, the study will be stopped, and 2 mg/day will be declared the MTD.
- e. If the 2 or more subjects are in Cohort D, the study will be stopped, and 5 mg/day will be declared the MTD.

Scenario 3: Hemoglobin > 12 mg/dL in a subject sustained for more than 7 days (not associated with RBC transfusion)

- Rule: The subject will be considered a complete responder, treatment will be discontinued, and the duration of the effect will be monitored until day 29 after start of treatment.

In addition to the stopping rules, a subject may be discontinued by the investigator at any time for failure to comply with protocol requirements, in the event that the investigator feels that continuation in the study poses a risk to the health of the subject, or if the subject withdraws consent.

The reason for treatment discontinuation must be documented in the subject chart / source records.

The trial will be stopped, as noted above, if more than one subject experiences the occurrence of the extrapyramidal symptoms, symptoms suggestive of tardive dyskinesia, neuroleptic malignant syndrome, the same SAE or treatment-emergent AE  $\geq$  Grade 3 felt to be causally related to TFP at the lowest dose level.

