## 6 Study Design

### 6.1 General Design

This study is a multi-center, Phase I/II, dose escalation, open-label study to determine the safety of TFP in adult subjects with DBA and RBC-transfusion-dependence. A 3+3 dose escalation regimen will be used. The maximum time on study drug will be 21 days with a 1 week post-treatment follow-up period. It is expected that up to 24 subjects can be recruited and complete the study within 12-18 months. The dose escalation study design is shown in Figure 1:

- If 2 or more of the 6 subjects in Cohort B demonstrate toxicity  $\geq$  Grade 3, the study will be stopped, and 1 mg/day will be declared the MTD.
  - If  $< 2$  of the 6 subjects in Cohort B demonstrate toxicity  $\geq$  Grade 3 within 21 days of starting therapy, Cohort C will start.
3. Cohort C: Three subjects will receive TFP 5 mg PO daily.
- If there is no toxicity  $\geq$  Grade 3 at the end of the 21 days, Cohort D will start.
  - If 1/3 subjects in Cohort C demonstrates toxicity  $\geq$  Grade 3, an additional 3 subjects will be enrolled in Cohort C:
    - If 2 or more of the 6 subjects in Cohort C demonstrate toxicity  $\geq$  Grade 3, the study will be stopped, and 2 mg/day will be declared the MTD.
    - If  $< 2$  of the 6 subjects in Cohort C demonstrate toxicity  $\geq$  Grade 3 within 21 days of starting therapy, cohort D will start.
4. Cohort D: Three subjects will receive TFP 10 mg PO daily.
- If 0/3 subjects in Cohort D demonstrates toxicity  $\geq$  Grade 3, the study will be stopped, and 10 mg/day will be declared the MTD.
  - If 1/3 subjects in Cohort D demonstrates toxicity  $\geq$  Grade 3, an additional 3 subjects will be enrolled in Cohort D.
  - If 2 or more of the 6 subjects in Cohort D demonstrate toxicity  $\geq$  Grade 3, the study will be stopped, and 5 mg/day will be declared the MTD.
  - If  $< 2$  of the 6 subjects in Cohort D demonstrate toxicity  $\geq$  Grade 3 within 21 days of starting therapy, 10mg/day will be declared the MTD.

Each subject will undergo safety assessments as per the required schedule while on the study drug. All dosed subjects will be followed for an additional 1 week after discontinuing study drug (post-study safety follow-up). There will be no more than 6 subjects enrolled at any particular time.

Treatment will be discontinued for any subject if their Hb is > 12 gm/dL, not associated with RBC transfusions.

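### In the visible text, one TFP-related death, life-threatening event or NMS case stops only the affected subject; no event-triggered hold on new dosing, expansion or escalation follows

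*Combined protocol and SAP*

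**What the plan says.** **Single events.** Section 15.4, Scenario 1, applies when one subject has extrapyramidal symptoms, signs suggesting tardive dyskinesia, NMS, or any SAE or Grade 3 or higher event attributed to TFP. The definition in 15.1 counts death and life-threatening events as SAEs. The one rule is "Treatment will be immediately stopped in that subject and the subject will be discontinued from the study".

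**Repeated events.** Scenario 2 needs more than one subject and, for SAEs and graded events, the same event. Rules b to e then act cohort by cohort, for example "If the 2 or more subjects are in Cohort C, the study will be stopped, and 2 mg/day will be declared the MTD".

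**Dose decisions.** Section 6.1 uses one threshold, toxicity of Grade 3 or higher, with no separate provision for Grades 4 and 5.
- After 1 of 3 in Cohort C, "an additional 3 subjects will be enrolled in Cohort C"; Cohort D has the same step.
- With fewer than 2 of 6 affected, Cohort B leads to Cohort C ("Grade 3 within 21 days of starting therapy, Cohort C will start") and Cohort C to Cohort D ("Grade 3 within 21 days of starting therapy, cohort D will start"). In Cohort D the result is "Grade 3 within 21 days of starting therapy, 10mg/day will be declared the MTD".

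**Oversight.** Section 3.5.1 schedules an interim safety analysis once the first 3 subjects of a cohort have finished 21 days. Section 15.1 requires SAEs to be reported within 24 hours. Section 15.6 gives the medical monitor a quarterly review, or an earlier one as needed for SAEs, and has the IRB and FDA told within 24 hours of a serious event needing rapid action. The investigator may also withdraw a subject "in the event that the investigator feels that continuation in the study poses a risk to the health of the subject".

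**The concern.** A 3+3 count is built for toxicities that are expected and tolerable in small numbers. A related death or NMS is a different kind of event. The usual response is to stop starting new subjects until someone independent has looked at the case. Here the visible rules move from the event to the next subject by count alone, and a pause depends on the judgement of the investigator, monitor, IRB or FDA.

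Three features of this trial add weight. Section 2 declines staggered dosing and gives safety monitoring as one reason, pointing to stopping rules in Section 6. The principal investigator is also the sponsor (Section 5), so much of the discretion rests with one role. Section 6.1 calls the study multi-center, and an unwritten pause is harder to rely on across sites. Section 10 itself describes NMS as potentially fatal.

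**Working it through.** **1. The plan's own figure.** Section 14.1 gives 3 to 24 subjects. Four cohorts × 6 = 24, and one cohort stopped at its first 3 gives 3. Both reproduce, so each cohort is 3 subjects, expandable to 6.

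**2. One related death in the first subject of a cohort.** Section 15.4 stops that subject. Section 6.1 records 1 of 3. The upper limits on later dosing are then:

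| Cohort | Rest of first 3 | Expansion | Same dose | Higher cohorts | Total |
|---|---|---|---|---|---|
| B (2 mg/day)* | 2 | 3 | 5 | 6 + 6 = 12 | 17 |
| C (5 mg/day) | 2 | 3 | 5 | 6 | 11 |
| D (10 mg/day) | 2 | 3 | 5 | 0 | 5 |

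*Assumes that the Cohort B expansion rule, which is not in the visible text, matches Cohort C.

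These are ceilings. They require that the other two have not yet started when the event occurs and that no further toxicity stops the study. Clearing B raises the dose 5/2 = 2.5-fold, and clearing C raises it 10/5 = 2-fold.

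**3. Does any visible step hold dosing when the event occurs?**

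| Step | What it does | Event-triggered hold? |
|---|---|---|
| 15.4, Scenario 1; 3.5.2; 7.6.1 | Act on the affected subject | No |
| 3.5.1 interim analysis | Scheduled review after the first 3 finish 21 days; no hold criteria given | No |
| 6.1 deferral after 1 of 3 | Delays escalation by dosing 3 more at that level | No |
| 15.1 and 15.6 reporting | Notifies sponsor, IRB and FDA | No |
| 15.6 monitor review | As needed; recommends in writing | No; dosing is not made to wait |

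Two gaps follow. First, members of the first 3 not yet dosed can still be started, because the interim analysis comes only after all 3 finish. Second, 3.5.1 ties its analysis to the first 3, so no visible review step stands between the expansion subjects and escalation.

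The second gap has a boundary. Expansion happens only after one toxicity in the first 3. A Grade 3 or higher event in an expansion subject within 21 days is therefore the second of 6, and 6.1 stops the study. What remains open is an event in an expansion subject during the follow-up week. The condition for escalating counts only 21 days, while 15.1 collects events to 7 days after the last dose.

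**4. Split events.** Take one NMS case in Cohort B and one in Cohort C. Two subjects meet the heading of Scenario 2. Rule a stops those two. Rules b to e each require 2 or more in one named cohort, so none applies. The closing paragraph of 15.4 concerns the lowest dose only.

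**5. How often the rule would be needed.** The documents give no rate. With an assumed per-subject probability p and independent subjects, the chance of at least one event is 1 − (1 − p)^n, where n = 12 is four cohorts of 3 and n = 24 is the maximum:
- p = 0.1%: 1.2% (n = 12), 2.4% (n = 24)
- p = 1%: 11.4% (n = 12), 21.4% (n = 24)

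This shows how often a hold might be used, not the harm that it would avert.

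**The case against.** The strongest reply is that oversight is layered and the risk is low. The drug has 60 years of clinical use and the doses lie within or below the clinical range (Section 2). No more than 6 subjects are enrolled at once (6.1). SAEs are reported within 24 hours, and unexpected fatal or life-threatening events reach the FDA within 7 days. The monitor, IRB or FDA could stop the trial. All of this stands and limits the size of the point. It does not supply a rule that makes dosing wait.

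Four stronger readings are tempting and are not supported:

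- *New subjects would be dosed with no review at all.* Section 3.5.1 does require a safety analysis after the first 3, at the point where 6.1 decides on expansion. The gaps are the narrower ones above.
- *Escalation could follow directly on a death.* In the visible Cohort C and D rules, a Grade 3 or higher event in the first 3 delays clearing the dose until 3 more have been treated. That is added exposure rather than review, but it is a bar.
- *NMS could be graded below 3 and escape 6.1.* The protocol leaves grading to CTCAE version 5.0 and assigns NMS no grade, so this is speculation.
- *The plan has no such hold anywhere.* Sections 2 and 3.5.1 refer to Section 6 for details, and parts of Section 6.1, with Figure 1 and 15.3.1-15.3.2, cannot be read here. A hold could be written there. Against that, 15.4 can be read in full and presents its list as the stopping rules.

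**Conclusion.** The point holds for the visible text. A single TFP-related death, life-threatening event or NMS case has a subject-level consequence only. Section 6.1 treats it as an ordinary count of one, and no safeguard is an event-triggered hold. In Cohort C the rules then permit up to 11 further subjects (5 at the same dose, 6 at twice the dose); in Cohort D they permit up to 5. The split-cohort gap in Scenario 2 is separate and smaller.

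The conclusion assumes that the event is graded 3 or higher, falls in the first 3 subjects and is the cohort's only toxicity, and that the unread text contains no hold. Such an event is unlikely at these doses, and no figure here measures harm avoided. The case for change is that the rules, followed exactly, leave to discretion a pause that is simple to require.

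**What to change.** Add two or three sentences across 6.1 and 15.4:

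- After any fatal or life-threatening event attributed to TFP, any NMS case, or Scenario 2 events occurring in different cohorts, dosing of new subjects, expansion and escalation all pause.
- The pause ends only after the medical monitor's documented review and written recommendation under 15.6.
- That review also addresses whether subjects already on drug continue.

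This uses the monitor and reporting route already in place. The decision to resume stays a clinical judgement, which suits events too rare for a numerical criterion; what changes is that the judgement must come before the next new subject is dosed. The cost is a delay of days to weeks if such an event occurs, and none otherwise. If Figure 1 or the unread parts of 6.1 and 15.3 already contain a hold, a cross-reference from 15.4 may be enough for single events; the split-cohort case should still be checked.

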#### **3.5.1 Dose Escalation**

Up to 4 cohort dose levels of TFP will be studied: 1, 2, 5, and 10 mg/day for up to 21 days each, as tolerated. Cohort A will start at 1 mg/day, and the dose will escalate to 2 mg/day in Cohort B, 5 mg/day in Cohort C, and 10 mg/day in Cohort D. At the start of each cohort, 3 subjects will be enrolled, and an interim analysis (IA) for safety and tolerability will be

conducted after all 3 subjects have completed 21 days of treatment (See [Section 6 Study Design](#) for details). The 21-day time frame is based on the t1/2 from the healthy volunteer 5 mg single dose TFP study ([Midha, 1983](#)), showing that TFP's elimination t1/2 is approximately 12-14 hours. Therefore, steady state is reached approximately 3 days after initiating therapy, and 21 days of therapy provides at least 18 days of exposure at steady state (the 1 and 2 mg doses likely have shorter t1/2 and so steady state will be reached even sooner in the first 2 cohorts).

Whereas some FIH trials may use an enrollment restriction rule such that only two subjects are dosed at a time, this trial will not use such an enrollment restriction design. Please see [Section 2 Brief Summary of Research](#) for the supporting rationale.

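### Sections 6.1 and 15.4 (Scenario 2) both stop the study and set the MTD but count different events, and no available text says which one governs.

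*Combined protocol and SAP*

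**What the plan says.** Section 6.1 sets out the 3+3 rules by cohort, and the event it counts is toxicity of Grade 3 or higher. For Cohort C, if no such toxicity has occurred, the instruction ends "Grade 3 at the end of the 21 days, Cohort D will start". For Cohort D, with none of three subjects affected, it ends "Grade 3, the study will be stopped, and 10 mg/day will be declared the MTD". Section 3.5.1 places the interim safety analysis at the end of dosing: it is to be "conducted after all 3 subjects have completed 21 days of treatment".

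Section 15.4 gives a second set of stopping rules. Scenario 1 concerns a single subject. It lists extrapyramidal symptoms, signs of tardive dyskinesia, and "neuroleptic malignant syndrome or any SAE or treatment-emergent AE" of Grade 3 or higher judged related to TFP. Scenario 2 concerns more than one subject. It opens "The occurrence of the extrapyramidal symptoms, symptoms suggestive of tardive dyskinesia (including vermicular movements of the tongue), neuroleptic malignant syndrome or the same SAE", continues with treatment-emergent AEs, and closes "Grade 3 felt to be causally related to TFP in more than 1 subject". Its consequences include the MTD. Rule d reads "If the 2 or more subjects are in Cohort C, the study will be stopped, and 2 mg/day will be declared the MTD" and rule e reads "If the 2 or more subjects are in Cohort D, the study will be stopped, and 5 mg/day will be declared the MTD".

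Neither section cites the other in the text available. Section 2 sends the reader to Section 6 alone for the cohort stopping rules.

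**The concern.** Two sections make the same decision from different counts. Section 6.1 asks only about grade. Section 15.4 names a neurologic class with no grade attached to it, and for other events it adds a causality judgement and a requirement that the event be the same one in each subject. A cohort can therefore meet one rule and not the other.

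The MTD is a stated objective in the Study Summary, and Section 2 singles out extrapyramidal and CNS effects for monitoring. If the two rules part on that event class, the declared MTD depends on which page the team opens. Choosing the page after seeing the data would make the result discretionary.

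**Working it through.** **Design check.** Section 14.1 gives 3 to 24 subjects. One cohort of three gives 1 × 3 = 3, and four cohorts of six give 4 × 6 = 24. The stated range reproduces. No power calculation applies.

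**Reading the trigger.** The question is whether the Grade 3 condition in Scenario 2 applies to the neurologic events or only to the SAE/AE items at the end of the list. Two points favour the second reading:
- Scenario 1 names the neurologic events beside any related event of Grade 3 or higher. If the grade applied to the whole list, naming them would be largely redundant.
- The list includes vermicular tongue movements, which Section 10 describes as a possible early sign of tardive dyskinesia. An early sign fits poorly with a Grade 3 floor.

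**The two rules on the same data.** Each row is one cohort of three subjects.

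| Pattern | Section 6.1 | Section 15.4, Scenario 2 |
|---|---|---|
| Cohort D: two with low-grade extrapyramidal symptoms, none Grade 3 or higher | Stop, MTD 10 mg/day | Stop, MTD 5 mg/day |
| Cohort C: same pattern | Start Cohort D | Stop, MTD 2 mg/day |
| Two with the same related Grade 3 event | Stopping count met | Stop |
| Two with different related Grade 3 AEs (not the named neurologic events) | Stopping count met | Not triggered |
| Two with unrelated Grade 3 AEs (not the named neurologic events) | Stopping count met | Not triggered |

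Only the first two rows are opposite instructions. In the last two, 15.4 is silent and does not tell the trial to continue.

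**How often the first two rows could arise.** The documents give no rate. Let p be the assumed per-subject chance of a low-grade neurologic event that 15.4 would count, with subjects independent and no toxicity of Grade 3 or higher. The chance of two or more among three is

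q = 3p²(1 − p) + p³

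- p = 0.02: 3 × 0.0004 × 0.98 + 0.000008 = 0.00118
- p = 0.05: 3 × 0.0025 × 0.95 + 0.000125 = 0.00725
- p = 0.10: 3 × 0.01 × 0.90 + 0.001 = 0.02800

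If Cohorts C and D are both run with three subjects, the chance of at least one conflict is 1 − (1 − q)², which gives 0.00237, 0.01445 and 0.05522.

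Requiring that no subject has Grade 3 toxicity, at an assumed independent rate of 5%, multiplies q by 0.95³ = 0.857. The per-cohort figures become 0.00102, 0.00622 and 0.02401.

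Setting q = 0.05 gives p of about 0.135, so the per-cohort chance reaches 5% only at a per-subject rate of about 13.5%.

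**Where p is likely to lie.** Section 3.5 expects extrapyramidal symptoms to be less likely at 10 mg or below, and Section 3.4 reports a side-effect profile similar to placebo at 2–6 mg/day. Both point to the low end. Against that, Section 10 says dystonia can appear in the first days of treatment and at low doses. Section 3.4 also reports more akathisia than placebo at 15 mg/day, but that dose is above this trial's maximum, so it shows plausibility and not a rate.

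**The case against.** The strongest reply is that Section 15.4 is a safety stop laid over the escalation scheme, with either rule sufficient. Cohort D cannot start in a study that has stopped, so on this view the Cohort C contradiction disappears. Timing helps the argument. Affected subjects stop treatment and leave the study at once, so if two of three do so during dosing, the condition for the interim analysis (all three completing 21 days) is never met as written.

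This is a reasonable guess at intent, but no available sentence says it, and Section 2 points the other way by naming only Section 6. Nor does timing settle an event first found at Visit 3 on Day 22 (Section 9.4), when dosing has normally ended and the 6.1 check is due. Whether Scenario 2 still applies then is itself unclear, because its first rule presupposes that treatment is under way.

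Three limits stand:
- Figure 1, Cohort A and the start of Cohort B in Section 6.1 are absent from the extracted text. A definition or cross-reference there cannot be excluded.
- If the Grade 3 condition governs the whole Scenario 2 list, the worked example falls away, and the sections differ only on causality and on the same-event condition. The redundancy argument is not conclusive: neuroleptic malignant syndrome would usually qualify as an SAE on either reading.
- The probability is small on any rate the documents make plausible.

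**Conclusion.** The concern holds. On the more natural reading of Scenario 2, two stated decision rules give opposite outcomes on the same data: 10 against 5 mg/day in Cohort D, and escalation against a stop at 2 mg/day in Cohort C. The Cohort D conflict is the firmer of the two, because there both sections stop the study and still name different MTDs.

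The chance per three-subject cohort is about 0.1% to 3% for assumed per-subject rates of 2% to 10%, and more likely near the lower end. The case rests on the consequence for a stated objective and on the ease of repair, not on frequency. Confidence is medium, because it depends on how the list is parsed and on the part of Section 6.1 that could not be read. The point should be fixed, but it does not call the 3+3 design into question.

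**What to change.** Reconcile Sections 6.1 and 15.4 before the next cohort decision, in one of two ways:
- Write one toxicity definition covering the events, grade, attribution, whether the event must be the same across subjects, and the time window. Cite it in both sections.
- Keep both rules and add a sentence saying which prevails when they differ, including for events first found at or after Visit 3.

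In either case, state whether extrapyramidal, tardive-dyskinesia-type and neuroleptic malignant syndrome events count regardless of grade, and extend the cross-reference in Section 2 to include Section 15.4. If the unextracted part of Section 6.1 already settles the matter, citing it in 15.4 and Section 2 would be enough. Which events and grades should count is a clinical decision for the sponsor.

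The cost is a wording amendment, with no added subjects or procedures.
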